Subject Payment. The payment schedule is detailed below. Subjects will be paid the medication compliance, study visit bonus, and participation earnings at the end of each experimental day (M, W, F). Subjects will receive an additional bonus (\$50) for completing of the study. Total possible payment for meeting all study requirements and collecting all bonus payments will be \$337.

Medication compliance. \$2 for each metric: 1) Medical Event Monitoring System (MEMS) bottle opening, (2) pill counts (empty bag), (3) positive riboflavin markers, and (4) text reply to reminder. Absence of each will result in payment not being earned for that specific metric. Total possible payment = \$8 per day X 14 study days = **\$112**. **Study visit bonus.** \$10 for on time arrival and providing an alcohol-free breath sample and urine sample. Total possible payment = \$10 per day X 7 visit days = **\$70**.

Participation. Total possible payment = \$15 per day X 7 visit days = **\$105**. **Completion bonus \$50**.

Subject participation requirements. Subjects must take the medication as close as possible to 10:00 PM each evening, and reply “yes” to the medication text prompt (texts will be sent at 15-minute intervals from 9:45 PM to 10:30 PM). On M, W, F over 2 consecutive weeks (see Study Design), subjects will visit the lab at 10 AM. At every visit, they will provide the following: medication update (MEMS bottle), side effects data questionnaire, med check up with nurse, UA fluorescence and toxicology, sleep data (wrist monitor and sleep questionnaire), and stress/anxiety questionnaires. The visit will take approximately 1 hour. In addition, on each Monday (day 1, 7, and 14) subjects will complete: (1) the cold pressor test (with cardiovascular measures and saliva sample for cortisol level), (2) the saccade-based attentional bias test, and (3) the cocaine cue reactivity questionnaire. On these three study days, the visit will take approximately 2 hours.

Data Safety Monitoring Plan

E1. Human Subjects Involvement and Participant Characteristics

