Exclusion criteria will include: (1) current DSM-IV diagnosis of any psychoactive substance dependence other than cocaine, marijuana, or nicotine; (2) have a DSM-IV axis I psychiatric disorder or neurological disease or disorder requiring ongoing treatment and/or making study participation unsafe; (3) significant current suicidal or homicidal ideation; (4) medical conditions contraindicating administration of suvorexant (e.g., severe pulmonary disease, severe cardiovascular disease or clinically abnormal EEG, severe liver or kidney disease, seizure disorder, or sleep disorder – particularly narcolepsy); (5) taking medications known to have significant drug interactions with the study medication(s) (e.g., MAO inhibitors, anticonvulsants, haloperidol, phenothiazines, anesthetics, and all sedatives); (6) currently or recently (last 3 months) treated for substance use [other than cocaine or nicotine] or another psychiatric condition; (7) conditions of probation or parole requiring reports of drug use to officers of the court; (8) impending incarceration; (9) pregnant or nursing for female patients; (10) inability to read, write, or speak English [required for lab tasks and psychometric scales]; (11) unwillingness to sign a written informed consent form; (12) subjects with alcohol use disorders or are drinking > 7 alcoholic drinks per week. All subjects who are excluded will be given referral information to other local treatment programs.

E2. Sources of Materials.

We will obtain information about subjects from structured interview evaluations, physical examinations, self-report measures, and computerized behavioral tasks. This information will be collected at specified time points during the study phases of intake, baseline assessment, experimental testing, and end-of-study. The biological specimens obtained from all subjects will include urine, saliva for cortisol assessment, and breath samples for alcohol detection. Individuals who volunteer to participate will be assigned a subject number (e.g., 10500), under which all information collected will be filed. All materials will be obtained for the specific purposes of this research.

E3. Potential Risks

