Risks for Cold Pressor Test. Individuals with cardiovascular disorders and neurological disorders should not participate. This information will be obtained during medical screening. Due to individual variation in pain and cold sensitivity, for some subjects the cold water may become too painful to sustain immersion for 90 seconds. There are no lasting effects from placing the hand and wrist in ice water (0° Celsius) for 90 seconds.

Risks for Physical Examination. There is a slight risk of bruising and infection in the blood draw procedures. This draw and the intake screening and physical exam are part of the CNRA General Evaluation protocol, and are approved under protocol HSC-MS-05-0322 and detailed therein.

E4. Adequacy of Protection Against Risks

Procedures to Minimize Drug-Related Risks.

We will screen very carefully for alcohol use and depressive symptoms. It will be made explicit that participants are not to drink alcohol in evening. We will use the Alcohol Use Disorders Identification Test (AUDIT) score and our mental health counselors SCID-screeners to enroll only those with low risk for alcohol abuse. Subjects will report no current depressive symptomatology (Beck Depression

Inventory, or BDI < 15), with no past depressive episodes or suicidal ideation. The Columbia Suicide Severity Rating Scale (CSSRS) will be administered at each visit (see additional details below), as per NIH/FDA guidelines. Indication of regular alcohol use by AUDIT score, intake self-report, or breath alcohol, or indication of increase in depressive symptomatology / suicidality as measured by the CSSRS will result in study stopping (see details below). Will exclude for any patients taking CYP3A inhibitors; patients with severe hepatic impairment; and women who are or become pregnant. Pregnancy and drug tests are administered on via urinalysis on lab testing days. Women of childbearing capacity must be taking one form of birth control. We will exclude for women with BMI > 30 to decrease risk of side effects, although it should be noted that in our cocaine use disorder population, we rarely encounter obese patients.

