Other Protections Against Risk. The following procedures will be taken to safeguard against adverse medication events: (1) careful initial intake evaluation to determine eligibility based on inclusion/exclusion criteria; (2) thorough physical evaluation prior to treatment, consisting of physical examination, standard laboratory tests, electrocardiogram, toxicology screen, pregnancy test, and vital signs; (3) repeated tests during treatment; (4) daily monitoring of pill taking using MEMS caps, returned pill counts, and self-report; (5) weekly review of adverse events and medication compliance; (6) regular evaluation by the study physician ([name]). Specific criteria will be used to exclude potential subjects for whom any of the study medications is contraindicated. Any abnormal physiological, psychological, or behavioral event will be evaluated and, if indicated, will result in the subject's removal from the study.

For all three experiments included in this project, we will use an Adverse Event Log (AEL) based on NIDA SAFTEE procedures. The AEL will record the duration, severity, and frequency or any adverse events, signs, and symptoms. An evaluation will be made as to the event's relationship to the study drug(s), scaled as unrelated, unlikely, possible, and probable. The AEL will be included in the report to DSMB.

Subjects will be monitored regularly for compliance with the study requirements, including the dosing regimen and breath alcohol testing upon arrival at the laboratory each day of testing. Written and verbal information about the medication will be given to all participants. This information will remind the subject to: (1) take food shortly after medication if needed to relieve gastric irritation; (2) inform the treatment research clinic nurse or physician of any over-the-counter and prescription medication taken, especially: cough medication, diarrhea medication, narcotic medication; (2) notify treatment research clinic nurse or physician of any side effects that persist or worsen. The study physician, nurse, and PI will review cases involving clinical deterioration of increased symptomatology or substance abuse. Appropriate actions will be taken, including study termination with proper referral.

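### The only alcohol stopping-rule input scheduled on treatment is a 10 AM breath test, which would be expected to read zero after one or two drinks the evening before

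*Combined protocol and SAP*

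**What the plan says.** The alcohol stopping rule is in E4, Procedures to Minimize Drug-Related Risks. Its inputs are "Indication of regular alcohol use by AUDIT score, intake self-report, or breath alcohol". The same section presents AUDIT, together with the diagnostic interview, as a way to enrol people at low risk, and schedules no repeat. It also sets the on-study instruction: "It will be made explicit that participants are not to drink alcohol in evening".

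The breath test is described in E4, Other Protections Against Risk, as "breath alcohol testing upon arrival at the laboratory each day of testing". Subject Payment ties a $10 bonus on each of 7 visit days to "for on time arrival and providing an alcohol-free breath sample and urine sample". Under Subject participation requirements, "subjects will visit the lab at 10 AM" on Mondays, Wednesdays and Fridays. Study design sets the dose at 10 PM nightly.

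The visit contents include "side effects data questionnaire, med check up with nurse, UA fluorescence and toxicology". None of these is itemised for alcohol, and the only urine analyte that E1 names is a cocaine metabolite.

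Entry is restricted: the E1 exclusions cover "subjects with alcohol use disorders or are drinking > 7 alcoholic drinks per week". Participants and setting gives a limit of 10 drinks a week and also excludes binge drinkers. Both that section and E1 contain a criterion on unwillingness to give up evening alcohol for the two study weeks. During the study, the physician, nurse and principal investigator "will review cases involving clinical deterioration of increased symptomatology or substance abuse", and that review can end participation.

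**The concern.** E3 says the risks of suvorexant rise with alcohol, and E10 describes the interaction as potentially dangerous because of sedation. That is why evening drinking is forbidden. People who drink up to the weekly limit may still enrol, so some participants can be expected to be drinkers. If the one alcohol measure that feeds the stopping rule is taken the next morning or later, light evening drinking may leave no trace in it, and staff must rely on disclosure or visible signs.

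A secondary effect is on attribution. The Adverse Event Log grades each event's relationship to the study drug. Sleepiness or poor coordination is harder to grade if nobody has asked about drinking the night before.

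**Working it through.** **1. Inputs available on treatment.** Of the three named inputs, AUDIT is an enrolment screen and the self-report is at intake by its own description. Breath alcohol is the only one scheduled after the first dose. E4 points to details below, but those that follow concern suicidality. No breath threshold, number of positives or definition of regular use is given for alcohol.

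**2. Time from dose to next breath test.** There are 14 doses at 10 PM, from Monday of week 1 to Sunday of week 2. Visits are at 10 AM on Mon, Wed, Fri, Mon, Wed, Fri, Mon. The first Monday precedes dosing, which leaves 6 post-dose tests.

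| Dose night | Next test | Gap | Nights |
|---|---|---|---|
| Tue, Thu, Sun | next morning | 12 h | 6 |
| Mon, Wed, Sat | second morning | 36 h | 6 |
| Fri | Monday | 60 h | 2 |

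**3. What a test can still detect.** The documents give no clearance figures, so these inputs are assumptions: 14 g ethanol per drink; distribution factor r of 0.68 (men) or 0.55 (women); elimination of 0.010 to 0.025 g/dL per hour; drinking ends at 10 PM, or at midnight as a sensitivity case. Elimination while drinking is ignored, which makes detection look easier than it is.

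Rise per drink (g/dL) = 14 / (r × kg × 10):
- 80 kg man: 14 / 544 = 0.0257
- 70 kg woman: 14 / 385 = 0.0364
- 55 kg woman: 14 / 302.5 = 0.0463

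Drinks needed to read above zero = hours × elimination rate / rise per drink. Hours to clear two drinks = 2 × rise per drink / elimination rate.

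| | 80 kg man | 70 kg woman | 55 kg woman |
|---|---|---|---|
| Drinks needed at 12 h, full rate range | 4.7–11.7 | 3.3–8.3 | 2.6–6.5 |
| Drinks needed at 10 h (ends midnight), slowest rate | 3.9 | 2.75 | 2.2 |
| Drinks needed at 36 h, slowest rate | 14.0 | 9.9 | 7.8 |
| Hours to clear two drinks | 2.1–5.1 | 2.9–7.3 | 3.7–9.3 |

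- *One or two drinks:* the longest clearance is 9.3 h, which is under 10 h. They read zero in every case, including drinking that ends at midnight.
- *Three drinks:* these register only if elimination is below 3 × rise per drink / hours. At 12 h the cut-offs are 0.0064 (man), 0.0091 (70 kg woman) and 0.0116 (55 kg woman), so only the last falls inside the assumed range. At 10 h they are 0.0077, 0.0109 and 0.0139, so both women can register at the slow end.
- *Four to five drinks:* these can register at the slow end on 12-hour nights.
- *The other 8 nights:* at least 7.8 drinks ending at 10 PM are needed.

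**4. Patterns inside the entry limit.** One drink on 7 evenings is 7 a week; two drinks on 3 evenings is 6 a week. Neither exceeds 7. Each evening's alcohol clears within 9.3 h, so nothing carries over to the next. Both patterns would be expected to read zero at all 6 post-dose tests.

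**The case against.** The strongest reply is that the rule is not aimed at every evening drink. Its trigger is regular use, and E10 treats more than 7 drinks a week as frequent. The two patterns above sit inside that limit, so they might not trigger stopping even if seen. This stands in part. The instruction and the rule are separate, and these patterns clearly breach only the instruction. With regular left undefined, though, a drink on every dosing night plausibly qualifies.

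Second, there are real safeguards: the screening limits, the criterion on willingness to stop evening alcohol, the instruction, the payment for a clean breath sample, the impairment battery and the case review. These lower the risk. But the willingness criterion is joined to the weekly limit by an *and* that leaves its reach unclear; the battery detects impairment at the visit, not drinking 12 to 60 hours earlier; and the review needs drinking to be disclosed or noticed.

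Third, a reader might infer that nobody asks about alcohol after enrolment. The documents do not support that. The nurse check, side-effects questionnaire and urine panel are not itemised and may touch on it, and E2 says interviews and self-report measures continue during testing. What can be said is that none is specified as an input to the rule.

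Fourth, a recall item also depends on disclosure. That is true; the gain is a prompted answer instead of a volunteered one.

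**Conclusion.** The point holds as a small safety-monitoring gap. The schedule gaps follow from the documents. The finding that one or two drinks finished by midnight read zero rests on the assumed clearance inputs, and holds across the whole range shown.

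Two stronger readings are tempting and should be resisted. One is that the rule is blind to moderate drinking generally. The figures do not show that: three drinks can register in a lighter woman with slow elimination, and four to five can register at the slow end on 12-hour nights. The other is that the treatment comparison is biased. The instruction and breath test apply equally in both blinded arms, and nothing in the documents points to a difference between arms.

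The documents give neither a rate of evening drinking on study nor the size of the added risk at one or two drinks. How often this matters is therefore unknown. The change is a cheap improvement, not a condition for running the trial.

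**What to change.** Add one item to the existing nurse or side-effects check at the 6 post-dose visits, asking about evening drinking on each night since the last visit. That is 2 nights at Wednesday and Friday visits and 3 at Monday visits: 2 + 2 + 3 + 2 + 2 + 3 = 14, so every dosing night is covered. Name the item in E4 as a trigger for same-visit review by the nurse or medical director, who decides whether to counsel or stop. Keep the breath test for heavy, late or morning drinking.

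Stopping should not be automatic, and the report itself should not reduce payment. Under the Subject Payment schedule, a participant stopped at a visit forgoes $8 × nights left + $25 × visits left + the $50 completion bonus, unless the sponsor decides otherwise:
- visit 2: 96 + 125 + 50 = $271
- visit 3: 80 + 100 + 50 = $230
- visit 4: 56 + 75 + 50 = $181
- visit 5: 40 + 50 + 50 = $140
- visit 6: 24 + 25 + 50 = $99

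Sums of that size could discourage honest answers.

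The cost is one question at visits already planned, with no added visit or procedure. The downsides are self-report error, dependence on disclosure, and possibly a few more participants stopped.

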Cue Reactivity: Cocaine Craving Questionnaire (CCQ)⁵⁵ is self-report 14-item measure with five conceptual domains: Desire to Use, Intention to Use, Anticipation of Positive Outcome, Anticipation of Relief from Dysphoria, and Lack of Control over use. The measure is well validated and has been used in multiple studies of CUD^{55,56}.

Sleep: Misfit Shine (Misfit © 2012). Sleep activity is monitored with a 3-axis accelerometer inside the watch device, using a general heuristic based on time and motion. The two primary data outcomes from sleep mode are total sleep and sleep quality (deep sleep duration). The device is waterproof and worn on the wrist 24 hrs per day. Data are downloaded to smartphone via Bluetooth.

Sleep: Pittsburg Sleep Quality Index (PSQI)⁵⁷. The PSQI is an 18-item self-report measure of sleep, providing a well-validated and reliable measure of sleep quality, latency, duration, duration efficiency, and disturbance, and an overall summary. It has been used in several studies of individuals with SUD, including cocaine^{21,58,59}.

Stress/Anxiety: Cold Pressor Test (CPT). The CPT reliably increases activity of the sympathetic nervous system and the HPA axis, and produces reliable increases in heart rate and cortisol^{75,76}. Subjects are requested to submerge the dominant arm up to the wrist or elbow in ice-cold water (0° to 4° C) for as long as possible with a maximum of 90 seconds. The procedure activates afferent nerves and elicits a CNS stress response^{75,76,77}. This procedure produces no lasting biological or psychological distress beyond the acute challenge period, and physiological effects return to baseline within 90 min⁷⁸. In fact, the CPT is used to study pain in children⁷⁹, and is considered a noninvasive, exempt educational experimental activity by the IRB of the University of Texas-Austin⁸⁰. It has been used extensively in cardiology, endocrinology, psychiatry, and psychology since 1940 as a challenge to the peripheral and central stress axis^{75,76}.

Stress/Anxiety: DASS21⁶⁰ is a 21-item self report questionnaire assessing the severity of clinically agreed upon core depression, anxiety, and stress symptoms. It is well validated in multiple languages and countries⁶¹, and has been utilized in SUD treatment and withdrawal studies⁶²⁻⁶⁴.

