In the event of either an unexpected adverse event or a prolonged period of intoxication, we have several measures in place. First, [name] (CNRA medical director) has clinical experience and training in emergency medicine. Thus, a physician will be in the immediate vicinity of laboratory at all times. Offices and clinical space are within 100 feet of the lab. Collaborating MDs can be paged at any time during the day. Second, Ben Taub Hospital, a level 5 emergency medical center is located just minutes away from BBSB. Finally, in the event of extended sedation, intoxication, or impairment, in which any subject does not appear clear-headed, feeling well, and in full control of his or her behavior, two steps will be taken. First, the subject will remain in the lab until such time that the primary or a co-investigator deems that it is safe for him or her to leave (e.g., passing the sobriety test described above). The large majority of our cocaine use disorder subjects use the METRO system, thus driving hazards are expected to be rare. However, in the event of extended impairment, we will arrange (and pay for) a taxi service to drive the subject back to his/her home rather than having to use METRO. We will administer the Columbia Suicide Severity Rating Scale (CSSRS screening version) at each visit to assess suicidality and depressive symptoms, consistent with current FDA best practices. If the screening indicates change in suicidal ideation, we will administer the full version. If suicidality is judged to clinically significant as per CSSRS scoring criteria, we will (1) report the event to CPHS within 48 hours; (2) remove the patient from the study; (3) make a referral to either the BBSB outpatient mood disorders clinic or UT HCPC, depending on consultation from Dept of Psychiatry outpatient faculty at BBSB.

For the cold pressor task, participants will be told that if the level of pain is too uncomfortable, they should remove the hand immediately and not wait to the end of the 90 sec test period. Each participant will be able to test the water temperature for 10 sec prior to beginning the procedure. These details are presented in the informed consent document. Because there are no sustained effects of cold water, if a participant cannot sustain the immersion for 90 sec on one test day, it will not preclude repeated testing on other lab test days (the cold pressor test will be repeated 3 times).

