3. Adverse events (AE) will be reported to the UT-CPHS on an annual basis. Serious adverse events will be reported immediately (verbally within 24 hours) to the UT-CPHS, the Monitoring Committee, and to the NIDA. A written report will follow as soon as possible but in no more than three days. The written report will be in the format required by the local IRB and will contain information regarding the date of the AE, description of the AE, severity rating (Grade 1 to 4), assessment of cause, whether the AE indicates an increased risk for current or future subjects, and whether changes to the informed consent form are necessary.

4. We will also use an ongoing Adverse Event Log (AEL) based on NIDA SAFTEE procedures. The AEL will record the duration, severity, and frequency or any adverse events, signs, and symptoms. An evaluation will be made as to the event's relationship to the study drug(s), scaled as unrelated, unlikely, possible, and probable. The AEL will be included in the report to DSMB.

E10. Specific Issues: NIDA / NACDA Guidelines on Administration of Drugs to Human Subjects.

Risk/Benefit. These issues are described in sections **E1 through E6**. As noted above, the potential for advances in scientific and treatment domains related to addiction are considerable. Based on the qualifications and long history of work in this area by the investigative team and the careful screening and monitoring for subject safety, we feel there is a favorable balance of potential benefit against risk.

Data Safety Monitoring Board is described in **E9**.

Informed Consent is described in section **E4**.

Subject Selection is described in section **E1**.

Confidentiality is described in section **E4**.

Medical and Psychological Screening and Services are described in sections **E1, E4, and E9**, as well as sections **D1 and D2** of the application.

Administration of Drugs to Individuals Who Have Never Used Drugs. Study drugs will not be

administered to subjects who have never used drugs. By definition all subjects will be individuals with substance use disorder (cocaine). Most of our subjects with cocaine use disorders also have an extensive history of use of other illicit drugs.

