The following procedures will be taken to safeguard against adverse medication events: (1) careful initial intake evaluation to determine eligibility based on inclusion/exclusion criteria (including exclusion for alcohol use disorder or frequent regular use); (2) thorough physical evaluation prior to treatment, consisting of physical examination, standard laboratory tests, electrocardiogram, toxicology screen, pregnancy test and vital signs; (3) repeated tests during treatment; (4) daily monitoring of pill taking using MEMS caps, returned pill counts, and self-report; (5) weekly review of adverse events and medication compliance; (6) evaluation by the study physician ([name]). Specific criteria will be used to exclude potential subjects for whom any of the study medications is contraindicated. Any abnormal physiological, psychological, or behavioral event will be evaluated and, if indicated, will result in the subject's removal from the study.

For this project, we will use an Adverse Event Log (AEL) based on NIDA SAFTEE procedures. The AEL will record the duration, severity, and frequency of any adverse events, signs, and symptoms. An evaluation will be made as to the event's relationship to the study drug, scaled as unrelated, unlikely, possible, and probable. The AEL will be included in the report to DSMB. Relevant information is also included in section E9.

Referral to Treatment. As noted above, at study end subjects will receive a follow up medical examination and a session with a masters-level licensed counselor or RN in our treatment research

clinic, who will provide information about treatment options and referrals. If depression or suicidal ideation is measured at risk during the study, participation will be terminated and appropriate referrals made (see above).

Incomplete Disclosure. We have no elements of deception in this project, other than withholding of dose information to subjects about dose contents on days of testing (e.g., suvorexant or placebo). However, informed consent documents will contain full disclosure of the drug that may be received during the course of the experiments, along with potential side effects. No information about study risks will be withheld from subjects.

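### The participant stopping rule for worsening depression or suicidality is stated three ways that disagree for depressive worsening and for suicidality below clinical significance

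*Combined protocol and SAP*

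**What the plan says.** E3 (Potential Risks) lists worsening mood and suicidal thoughts among the precautions for suvorexant. Three later places say what follows if this happens on study.

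- **E4, Procedures to Minimize Drug-Related Risks:** an "indication of increase in depressive symptomatology / suicidality as measured by the CSSRS will result in study stopping". The sentence sends the reader to details further on.
- **E4, the paragraph on unexpected adverse events and prolonged intoxication**, which appears to be those details: "We will administer the Columbia Suicide Severity Rating Scale (CSSRS screening version) at each visit to assess suicidality and depressive symptoms". Next, "If the screening indicates change in suicidal ideation, we will administer the full version". The removal step is: "If suicidality is judged to clinically significant as per CSSRS scoring criteria, we will (1) report the event to CPHS within 48 hours". The participant is then taken out of the study and referred.
- **E10, Referral to Treatment:** "If depression or suicidal ideation is measured at risk during the study, participation will be terminated". Referral follows, with a pointer back to earlier text.

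E4 (Other Protections Against Risk) adds a case review by the study physician, nurse and principal investigator when a participant deteriorates, which can lead to termination. The same section and E10 also say that any abnormal event, psychological ones included, is evaluated and leads to removal where indicated.

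On reporting, E9 item 3 says: "Serious adverse events will be reported immediately (verbally within 24 hours) to the UT-CPHS, the Monitoring Committee, and to the NIDA". A written report is due within three days. Other adverse events go to CPHS once a year.

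Two further depression measures appear. The BDI is an entry criterion (below 15). The DASS21 is described under Measurements as a "21-item self report questionnaire assessing the severity of clinically agreed upon core depression, anxiety, and stress symptoms" and is classed there as a stress/anxiety measure. Neither is linked to a stopping step.

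**The concern.** A stopping rule should give the same answer whichever section a nurse or physician opens. Here the general statement in E4 covers depression and suicidality and acts on any increase. The steps that appear to carry it out leave depression out and act only at a higher level. E10 brings depression back without saying how it is measured.

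Safety comes first: the protocol names worsening depression as a drug risk and says participation will end for it, but it gives no defined route for doing so when suicidality is absent. There is also a cost to the data. In a double-blind, two-arm study that enrolls 45 to complete 30, withdrawals that depend on which section staff follow are not governed by one prespecified rule.

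**Working it through.** No figure in the plan bears on this point, so the check compares the text.

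**Step 1. The three statements side by side**

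| | E4, general statement | E4, later steps | E10, Referral to Treatment |
|---|---|---|---|
| Covers depression? | Yes | Named as a purpose of the CSSRS, but no step acts on it | Yes |
| Covers suicidality? | Yes | Yes | Yes (ideation) |
| Instrument | CSSRS | CSSRS screener, then full version | None named |
| Threshold | Any increase | Clinically significant by CSSRS scoring; no cut-off written out | At risk; not defined |
| Action | Stopping | Report, removal, referral | Termination, referral |

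The general statement does not say whether it is the participant or the trial that stops. The context points to the participant, and I read it that way.

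**Step 2. Three hypothetical participants**

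| Participant | E4, general statement | E4, later steps | E10 |
|---|---|---|---|
| A. Clinically significant suicidality | Stopped | Removed | Terminated |
| B. CSSRS increase, not clinically significant | Stopped | Full CSSRS if ideation has changed; removal criterion not met | Depends on the undefined threshold |
| C. Worse depression, no suicidality | Stopped only if the CSSRS registers it | No step applies | Terminated if judged at risk; no measure given |

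A gets one answer. B is stopped under the general statement but does not meet the removal criterion in the later steps. C may be terminated under E10 but has no removal step in the later E4 text. For C, what remains is the discretionary review and removal in E4 (Other Protections Against Risk) and E10.

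The cross-references do not settle this. They suggest that one rule was intended, with the later E4 steps as its working detail. Following them leads to text that drops depression and raises the threshold.

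**Step 3. Reporting, by seriousness**

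| Event | E4 steps | E9 item 3 | Compatible? |
|---|---|---|---|
| Clinically significant suicidality, not an SAE | CPHS, 48 hours | CPHS, annually | Yes; E4 is an added, faster report |
| Clinically significant suicidality that is also an SAE | CPHS, 48 hours | CPHS, Monitoring Committee and NIDA, verbally within 24 hours | No; the governing rule is not stated |

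In the second row the clocks differ by 48 − 24 = 24 hours, and the recipients by 3 − 1 = 2 bodies. No section defines an SAE or says whether a CSSRS-triggered removal counts as one.

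**The case against.** The strongest reply is that these passages are one rule stated at different levels of detail. The general statement points forward and E10 points back. The later E4 steps give a workable sequence of screener, full version, clinical judgement, removal and referral, and for clinically significant suicidality every version ends participation. That last part stands. The later steps also do not say that a participant below the threshold continues; they only fail to remove that participant. But the reply does not supply the missing depression step, and it does not reconcile any increase with clinically significant.

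Four stronger readings are tempting, and the documents do not support them.

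- **Depression without ideation would trigger nothing and go unnoticed.** Subject participation requirements lists a side-effects questionnaire and nurse check at every visit. E4 and E10 provide weekly adverse event review, an adverse event log, and removal where indicated; E4 adds the case review of deterioration. E9 item 2 lets the Monitoring Committee recommend discontinuing an individual's medication. These are real routes to removal. They are discretionary and carry no depression measure or threshold, so they do not supply the defined stop that E10 promises.
- **The 24-hour and 48-hour clocks contradict each other outright and make the stopping rule unusable.** They differ only when the event is also an SAE, a report within 24 hours meets both time limits, and reporting has no bearing on whether a participant is stopped.
- **45 × 6 = 270 post-dose visits carry a depression score that nobody reviews.** The visit table and visit list name stress/anxiety data and questionnaires, not the DASS21, so its use at every visit is inferred. The product also assumes no dropout. If the 15 planned non-completers miss at least the last visit, the maximum is 30 × 6 + 15 × 5 = 255. Either count includes placebo participants and measures questionnaires, not participants at risk.
- **The DASS21 should therefore be the trigger.** The protocol presents it as a stress/anxiety measure, and choosing a clinical trigger is outside this review.

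It is also fair that entry criteria (BDI below 15, no past depressive episodes, other Axis I disorders excluded) and two weeks of treatment should make such events less frequent. That limits how often the conflict arises; it does not remove it.

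**Conclusion.** Wrong as written. The disagreement is confined to two situations: a CSSRS increase that is not clinically significant, and depressive worsening without suicidality. In the first, E4 contradicts itself. In the second, E10 provides for termination while the E4 steps have no matching action. The reporting mismatch is a separate and conditional finding, limited to suicidality events that are also SAEs.

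The conclusion assumes that the stopping sentence in E4 means the participant and that the later E4 paragraph is the detail it refers to. If that paragraph is not the intended detail, the general statement has no operating procedure for this trigger, and the need to reconcile remains. I take no view on which measure, threshold or clinical rule is right.

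**What to change.** Reconcile the general statement in E4, the later E4 steps, Other Protections Against Risk in E4, and Referral to Treatment in E10 into one participant stopping rule that the other sections cite. The sponsor and study physician should set the measure of depressive worsening and the threshold. The rule should also state whether the DASS21 depression score that the study already collects has any safety role.

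Separately, reconcile the E4 report with E9 item 3, so that the clock and recipients are clear for a suicidality event that is serious.

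The cost is protocol wording, and possibly a few more clinician reviews or withdrawals, depending on the rule chosen.
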